8.2.2 Control Intervention

Participants in the control intervention will receive SOC only in person at the baseline visit and then over the phone.

After this first visit, study nurses will contact participants in both study groups over the phone on the day of the target quit date, then again after 1 week, 2 weeks, 4 weeks and 8 weeks. During these follow-up calls, study nurses will provide SSC and ask participants about their use of tobacco cigarettes. Study nurses will record the time spent on the phone with each participant.

Average duration of counseling is expected to be 15 minutes over the phone and during the in-person visits at 6-, 12- and 24- month follow-up visits and 30 minutes during the in-person visit at baseline. Participants will be allowed to use other NRT, smoking cessation medication or smoking cessation help at their own expenses. Participants interested in other evidence-based smoking cessation drug therapy (varenicline or bupropion) will be allowed to consult their primary care physician (PCP) or another health professional to get a prescription for these drugs. They will also be encouraged to go on the stop-tabac.ch (www.stop-tabac.ch) website for smoking cessation support if they wish online support, as is currently performed in smoking cessation counseling in Switzerland.

8.3 Dose / Device modifications

Participants will be free to choose between four nicotine concentrations (0 mg/ml, 6 mg/ml, 11 mg/ml or 19.6 mg/ml), 6 flavors (two different tobacco flavors, menthol flavor or three different fruity flavors) and administered through ENDS ad libitum during the first 6 months of follow-up. They will have the possibility to switch to other predefined nicotine concentrations and flavouring in order to maximise the adherence to ENDS. We will teach them how to recognize withdrawal symptoms (changes in mood etc) and instruct them to use more liquid or a higher nicotine concentration if they experience withdrawal symptoms.

Criteria for discontinuing the study treatment or study discontinuation see section 7.4.

8.4 Compliance with study intervention

Study nurses will be trained to deliver a structured intervention that includes explanations on how to use the device and e-liquids. We will optimize adherence of study participants to ENDS by offering participants a choice of nicotine content and e-liquid flavors. This should maximize the effect of ENDS and more closely match real life, since smokers select products based on their own needs and preferences. We also allow participants the opportunity to switch e-liquid flavors, as real life consumers might. Second, in order to avoid participants stop using ENDS for technical reasons, study nurses will provide 2 devices at the baseline visit and be reachable during regular working hours. In case of defective ENDS-devices which need to be replaced, participants can either directly visit the centers to pick up replacement devices, or we will ship replacement devices directly to the participants' home as fast as possible.

We will monitor how many e-liquids containing bottles are distributed by the study nurses and participant's use of e-liquids in ml during follow-up calls after 1 week, 2 weeks, 4 weeks and 8 weeks after the target quit date and at the 6months visit. We will continue to monitor use of ENDS and e-liquids at the 12- and 24- months visit by monitoring the type of device they use and the type of e-liquids they use. During follow-up calls study participants will be asked about any problem with regard to using the ENDS. At the 6-, 12 and 24- months visit, we will verify participant exposure to tobacco cigarettes vs. other sources of nicotine (ENDS, NRTs, etc.) by measuring cotinine, anabasine, CO and NNAL.

We will offer a voucher ("BERNcity Geschenkkarte" or similar voucher for Lausanne, Geneva, Zürich and St. Gallen) worth CHF 50 at the baseline visit to participants in the control group. Requesting participants in the control group to avoid using ENDS for 6 months instead of 24 months should also limit the number of participants who will purchase an ENDS on their own in the control group or who are lost to follow-up. However, we will ask participants in the control group if they use an ENDS at each follow-up call and follow-up visit.

Participants in the additional MRT data collection at the 6 month visit will receive 90 CHF given that these are additional measures and that participants will need to come back on another day. The 90 CHF corresponds to 2X1.5 hours visits a 25 CHF per hour (75 CHF) and 15 CHF for transportation costs. Healthy volunteers will receive a voucher of 90CHF and a voucher for a lunch at the Inselspital, Bern.

At 12- and 24- months follow-up, we will offer a voucher to all participants coming for a personal visit worth 30 CHF in order to encourage them to come at the clinical visit in person to assess and validate outcomes.

Adherence to the allocated product is defined as not having used the non-allocated product on a minimum of 5 days during the last 7 days, on at least 1 visit.

8.5 Data Collection and Follow-up for withdrawn participants

A participant who decides to discontinue the study participation prematurely will be defined as a dropout if they have already been randomized. A study participant who terminates the study before being randomized will be defined as a screening failure.

Participants who cannot be reached over the phone at follow-up visits will not be excluded. Participants who do not present at the 6-, 12- and 24-month visits will be contacted by phone, by letter/e-mail, and, finally, we will contact their relatives or general practitioner. If we cannot contact participants for more than three months, we will consider them lost to follow-up.

In case of withdrawal, the biological material and health-related personal data of the person concerned will be anonymised after data evaluation has been completed.

8.6 Trial specific preventive measures

We will perform pregnancy tests in pre-menopausal women during the baseline visit. We will also specifically ask participants if they have known allergies to the tested products.

8.7 Concomitant Interventions (treatments)

Participants both in the control and intervention group will be allowed to use any NRT (patches, gums) or other smoking cessation medication (bupropion, varenicline) they wish at their own costs. Their use will be recorded in the eCRF and considered as a covariate in data analysis.

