6.2.2 Blinding procedures

Participants, nurses and investigators will not be blinded. We will blind both the statisticians who perform the main analyses and the laboratory personnel who determine urinary cotinine, anabasine, VOCs, TSNA (NNN, NNK and its metabolite NNAL) and PAHs (1- and 2-Naphtol and 1-OHP) levels.

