7. STUDY POPULATION

7.1 Eligibility criteria

Subjects fulfilling all of the following inclusion criteria are eligible for the study:

- Informed Consent as documented by signature
- Persons aged 18 or older
- Currently smoking 5 or more cigarettes a day, for a least 12 months
- Willing to try to quit smoking within the next 3 months
- Persons providing a valid phone number, a valid email address and/or a valid postal address.

The presence of any one of the following exclusion criteria will lead to exclusion of the subject:

- Known hypersensitivity or allergy to contents of the e-liquid
- Participation in another study with investigational drug within the 30 days preceding the baseline visit and during the present study where interactions are to be expected
- Women who are pregnant or breast feeding
- Intention to become pregnant during the course of the scheduled study intervention, i.e. during the first 6 months of the intervention
- Persons having used ENDS or tobacco heating systems regularly in the 3 months preceding the baseline visit
- Persons having used nicotine replacement therapy (NRT) or other medications with demonstrated efficacy as an aid for smoking cessation such as varenicline or bupropion within the 3 months preceding the baseline visit
- Persons who cannot attend the 6-month follow-up visit for any reason
- Persons who cannot understand instructions delivered in person or by phone, or otherwise unable to participate in study procedures

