9.3.2 Visit 1, Baseline visit at -7 days to target quit date

- Patient information and delivery of written study information to subject
- Verification of eligibility, including urine pregnancy test for premenopausal women
- Informed consent
- Demographics
- Relevant medical history including current medication
- Smoking history and symptoms linked to smoking, cigarette dependence (Fagerström Test for Cigarette Dependence), withdrawal symptoms
- Body weight, height, calculation of BMI, waist circumference
- Vital signs (heart rate, systolic and diastolic blood pressure at the right arm after at least 5 minutes at rest sitting)
- Questionnaires
 - Respiratory symptoms
 - Quality of life
 - Physical activity
 - Anxiety
 - Depression
 - Sleep quality
 - Alcohol and illegal drug use
 - Environmental pollution exposure
- Exhaled breath composition (CO, oxidative stress markers in a subset of participants)
- Blood collection (lipids, HbA1c (only for participants with diabetes) & creatinine, inflammatory biomarkers)
- Urine collection (nicotine metabolites, VOCs, PAHs, nitrosamines, oxidative stress markers)
- Randomization to study group
- Distribution and instruction of ENDS and e-liquids (intervention group only)
- Smoking cessation counselling

- Scheduling of phone calls
- Pulmonary function tests (conventional and MBW in a subset of participants)
- Micronuclei assessment in buccal epithelium
- Olfactory function: Burghart Sniffin' Sticks 16-Item Identification Test
- Inflammatory biomarkers
- .

9.3.3 Phone calls at target quit date, week 1, week 2, week 4, and week 8

Phone calls at target quit date (corresponding to day 0) and after 1 week (± 2 days), 2 weeks (± 3 days), 4 weeks (± 4 days), and 8 weeks (± 1 week):

- Smoking status: cigarettes / ENDS
- Assessment of smoking cessation medication use: NRT, proven effective drug therapies (varenicline, bupropion) and other interventions without demonstrated efficacy (e.g. acupuncture, hypnose, sophrology etc)
- Assessment of AEs, ENDS deficiencies
- Smoking cessation counselling
- ENDS technical trouble shooting
- Scheduling of phone calls and outcome visit

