11.4.2 Primary Analysis

To answer the primary research question, we will compare the rates of quitting among smokers randomized to ENDS vs. those receiving usual care, on an intention-to-treat basis. Continuous smoking cessation from target quit date will be the main outcome, confirmed by biomarkers of exposure (anabasine). We will calculate quit rates, relative risks (RR), and absolute risks for ENDS +SOC (intervention group) compared to SOC alone (control group). We will further compare groups using multivariate regression models adjusting for appropriate co-variates. Participants who stopped smoking, and who are continuous ENDS users, will be considered quitters.

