4.3 Estimands

4.3.1 Treatment policy estimand

Outcome of interest: The primary analysis of the primary outcome (binary) will focus on the treatment policy estimand,

Patient set of interest: using the full analysis set following the intention-to-treat principle, i.e. subjects will be analysed according to the randomized group, irrespective of the treatment actually received.

Intercurrent events: Intercurrent events will be disregarded. Missing values in the primary outcome will be categorized as persistent smoker (i.e. treatment failures).

Summary measure: The difference between the two groups will be presented as a relative risk.

The primary analysis of secondary outcomes will focus on the treatment policy estimand as well. Missing values in secondary smoking cessation outcomes will be treated as for the primary outcome. Missing values in other outcomes will be imputed. Effect sizes of binary outcomes will be presented as relative risk. Effect sizes of continuous outcomes will be presented as mean difference.

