5.6 Adherence and protocol deviations

Adherence

Adherence in the control group is defined as not having used an ENDS device on 5 or more days during the last 7 days of any visit.

Adherence in the intervention group is defined as having used an ENDS device on 5 or more days during the last 7 days of at least one visit.

Adherence will be presented in a table as number (and %) of patients not smoking cigarette, smoking cigarettes only, smoking ENDS only, and smoking cigarettes and ENDS for both groups at each time point (Weeks 1, 2, 4, 8, and month 6). In addition, the number (and %) of patients using any NRT (patches, gums) or other smoking cessation medication (bupropion, varenicline) during the 24 hours before the visit will be presented in a similar table.

Protocol deviations

Protocol deviations are defined in Table 1. All of these protocol deviations will be presented in a table with the number of patients (%) having a protocol deviation for the control and intervention group.

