6.3 Analysis methods

6.3.1 Primary analysis

The primary analysis is based on the treatment policy estimand, using the full analysis set according to the intention to treat principle.

The primary outcome will be presented as proportion with 95% Wilson confidence interval in each intervention group and compared between groups using the chi-square test. The effect size will be presented as relative risk with 95% Koopman confidence interval, as well as risk difference with 95% Newcombe-hybrid-score confidence interval.

Secondary smoking outcomes will be analysed as the primary outcome.

Continuous secondary outcomes will be analysed using linear models, adjusted for the outcome measure at baseline, if it is available. Missing values in continuous outcomes will be imputed. Thus, the estimates of the complete data models are averaged using Rubin's rule (Rubin 1987). Effect sizes will be presented as mean difference with 95% confidence interval.

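### On-study NRT and cessation-drug use, which allocation can change, is named as an analysis covariate; models of the randomised comparison that adjust for it would not estimate the SAP's treatment-policy effect

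*Supplement*

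**What the plan says.** **Protocol v9.0**

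- Section 8.7 permits NRT, bupropion and varenicline in both arms at the participant's own cost, and adds: "Their use will be recorded in the eCRF and considered as a covariate in data analysis".
- Section 11.4.2 (Primary Analysis) calls for quit rates, relative risks and absolute risks, then: "We will further compare groups using multivariate regression models adjusting for appropriate co-variates". It lists no covariates. Section 11.4.3 repeats these calculations for the secondary cessation outcomes, and 11.5 places the inverse-probability-of-censoring sensitivity analyses inside the multivariate models.
- Section 7.1 excludes recent users, in the criterion that begins "Persons having used nicotine replacement therapy (NRT) or other medications with" and covers the three months before the baseline visit.
- Section 9.3.3 collects use at the calls on the quit date and at weeks 1, 2, 4 and 8, under an item that begins "Assessment of smoking cessation medication use: NRT, proven effective drug therapies (varenicline, bupropion".
- Section 6.2.2: "Participants, nurses and investigators will not be blinded".
- Section 3.6 describes standard of care as including counselling on NRT and other effective cessation medication.

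**SAP v2.0**

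- Section 4.3.1 sets a treatment-policy estimand on the full analysis set: "Intercurrent events will be disregarded".
- Section 6.3.1 has the primary outcome "compared between groups using the chi-square test", with an unadjusted relative risk and risk difference. Secondary smoking outcomes are handled the same way.
- Section 5.6 only tabulates the number of patients "using any NRT (patches, gums) or other smoking cessation medication (bupropion, varenicline) during the 24 hours before the visit".
- Section 7 leaves further analyses to the principal investigator, as described in the protocol. Table 4, the list of changes from the protocol, does not withdraw the covariate in 8.7.

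**The concern.** A covariate in a model of a randomised comparison should be fixed before allocation. This one is not. One arm receives free nicotine ENDS and the other does not, both arms pay for NRT and drugs themselves, and everyone knows the allocation. Use of aids may therefore differ between arms because of the allocation.

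Two things follow if a model conditions on it. First, taking up NRT or medication is part of what standard of care is meant to bring about. Holding it fixed removes that part of the comparator's effect, so the model no longer answers the question of ENDS plus standard of care against standard of care. Second, whoever buys an aid may differ in motivation or dependence. Comparing arms within levels of use then compares groups that randomisation did not balance.

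At stake are the adjusted estimates reported beside the primary result, those for the secondary cessation outcomes, and the weighted sensitivity analyses. Section 8.7 names a covariate and 11.4.2 lists none, so an analyst filling the gap in 11.4.2 has been pointed to this one.

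**Working it through.** **1. Is the covariate post-randomisation?** Use in the three months before baseline is an exclusion (7.1). Randomisation takes place at the end of the baseline visit (7.3). Use is then recorded at calls from the quit date onwards (9.3.3). There is no recent pre-randomisation version to adjust for.

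**2. Does the plan's own figure depend on it?** Inputs from protocol 11.2: 12% v 19%, two-sided alpha 0.05, power 90%. With unpooled variance,

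n per group = (0.12 × 0.88 + 0.19 × 0.81) × (1.960 + 1.282)² / 0.07² = 557 (rounded up),

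which matches the stated 557. Then 1114 / 0.95 = 1172.6, stated as 1172. The calculation is unadjusted, so the sample size does not depend on aid use.

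**3. What would adjustment do?** The documents give no aid use by arm and no quit rate among users, so both are assumed. Let qC and qE be the proportions using aids, and let r be the ratio of quit rates, users to non-users, taken as the same in both arms. Keep the overall rates at 12% and 19%. The non-user quit rate in each arm is the overall rate divided by (1 − q + r·q). The RR is then the same in both strata, so the Mantel–Haenszel RR stratified on use equals

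RR(adj) = (0.19 / 0.12) × (1 − qC + r·qC) / (1 − qE + r·qE).

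The crude RR is 0.19 / 0.12 = 1.58 and the risk difference is 7.0 points.

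Examples with use at 30% control v 10% ENDS:

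- r = 1.5: 1.583 × 1.15 / 1.05 = 1.73 (stratified risk difference 8.3 points)
- r = 0.7: 1.583 × 0.91 / 0.97 = 1.49 (6.1 points)

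Range over assumptions (adjusted RR):

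| Use, control v ENDS | r = 0.7 | r = 1.5 | r = 2.0 |
|---|---|---|---|
| 30% v 30% | 1.58 | 1.58 | 1.58 |
| 30% v 10% | 1.49 | 1.73 | 1.87 |
| 50% v 10% | 1.39 | 1.89 | 2.16 |
| 60% v 5% | 1.32 | 2.01 | 2.41 |

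In every row the effect of assignment on quitting is the same: 19% against 12%. Only the conditioning moves the estimate. In this stratified model there is no shift when use is equal in the two arms or when r = 1.

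**The case against.** The strongest reply is that the specified analysis never uses this covariate. Protocol 11.4 hands the choice of models to the SAP. SAP v2.0 is later than protocol v9.0, its primary and secondary smoking analyses are unadjusted, its continuous outcomes adjust only for the baseline value, and aid use is only tabulated. That stands, and it sets the limit of the point.

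A second reply is that 8.7 says only that use will be considered, names no analysis, and that an appropriate covariate under 11.4.2 need not include it. The wording is indeed soft. But nothing says that the two sentences are unconnected, SAP section 7 leaves the further models to the protocol, and Table 4 does not drop the clause.

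Third, aid use has legitimate roles: in the exposure-group comparisons of 11.4.3, which are not randomised contrasts, and in modelling the censoring weights. This also stands, and the fix keeps those uses.

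Two stronger readings are tempting. A reader might infer that the main result is biased; the unadjusted primary test rules that out. A reader might also infer that adjustment favours ENDS, because controls have more reason to buy NRT. That needs aid users to be both more frequent among controls and more likely to quit. The documents give neither fact, and with users less likely to quit the shift goes against ENDS.

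**Conclusion.** Wrong as written, but only for the adjusted models. Section 8.7 names a post-randomisation variable that allocation can affect, and 11.4.2 leaves room for it in models of the randomised comparison. Such a model does not estimate the treatment-policy effect in SAP 4.3.1. The affected results are the adjusted estimates under 11.4.2 and 11.4.3 and the weighted sensitivity models under 11.5.

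That the adjusted model targets a different quantity follows from the documents alone. The size does not: every figure rests on assumed use by arm and an assumed relation of use to quitting. Over the cases shown, an RR of 1.58 becomes anything from 1.32 to 2.41, and it stays at 1.58 if use is equal. The figures also leave out unmeasured differences between users and non-users, which could add a shift of either sign. The point should be corrected, but it does not threaten the primary conclusion.

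**What to change.** - **Protocol 8.7:** replace the covariate clause with a statement that use of NRT and cessation medication will be tabulated by arm and visit, as SAP 5.6 already does, and will not be a covariate in models of the randomised comparison.
- **Protocol 11.4.2:** restrict covariates to pre-randomisation variables and name the set before the adjusted models are run. Which variables to choose is for the trial statistician. The same restriction then carries over to the outcome models in 11.4.3 and 11.5.
- **Permitted uses:** aid use may still enter analyses that are not randomised comparisons (the exposure-group models), the censoring-weight models, or a mediation analysis labelled exploratory with its own estimand.
- **SAP Table 4:** add one line recording the change, so that the protocol and SAP agree.

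The cost is a few sentences. No new data are needed, and the sample size stays at 1172.

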8.8 Study Device Accountability

The investigator or designee will maintain an inventory record of ENDS and e-liquids at the site level (received from manufacturer, returned to manufacturer) and at the patient level (dispensed to the patient, returned by the patient).

8.9 Return or Destruction of Study Device

Upon completion or termination of the trial, ENDS and spare e-Liquids will remain in the participants' possession, or if desired, can be returned to the sponsor.

9. STUDY ASSESSMENTS

9.1 Table of study procedures and assessments

Procedure	Screening ①	Baseline visit	Day 0 ①	Week 1 ①	Week 2 ①	Week 4 ①	Week 8 ①	Outcome Visit Month 6	Outcome visit Month 12	Outcome visit Month 24
Visit timing Day 0 is target quit date (TQD)	-x to -8 days	-7 days	Day 0 (TQD)	+ 7 days	+14 days	+ 28 days	+ 56 days	+ 180 days	+ 360 days	+ 720 days
Visit window				±2 days	±3 days	±4 days	±1 week	-4/+12 weeks	-4/+12 weeks	-4/+12 weeks
ENROLLMENT										
Eligibility screen	x	x								
Explanation of project and protocol	x	x								
Send informed consent	x									
Sign informed consent		x								
Randomization to ENDS (E) or control		x								
Set target quit date (TQD)	x									
ASSESSMENT										
Demographics	x	x								
Medical History		x						X*	X*	X*
Physical activity		x						X*	X*	X*
Smoking history	x	x								
Nicotine dependence		x						X*	X*	X*
Withdrawal symptoms		x						X*	X*	X*
Environmental pollution (e.g. second hand smoke)		x						X*	X*	X*
Alcohol and illegal drug use		x						X*	X*	X*
Anxiety		x						X*	X*	X*
Depression symptoms		x						X*	X*	X*
Sleep quality		x						X*	X*	X*
Quality of life		x						X*	X*	X*
Women: pregnancy test		x								
Pulmonary function tests and MBW		x						x	x	x
MRI of the lung+								x		
Micronuclei assessment in buccal epithelium		x						x	x	x
Olfactory function		x						x	x	x
"Dry-hit" recognition								E		
Inflammatory biomarkers		x						x		

Procedure	Screening ①	Baseline visit	Day 0 ①	Week 1 ①	Week 2 ①	Week 4 ①	Week 8 ①	Outcome Visit Month 6	Outcome visit Month 12	Outcome visit Month 24
INTERVENTION										
ENDS & e-liquid distribution		E								
E-liquid order by participants				E	E	E	E	E		
E-liquid sent to their homes					E	E	E	E		
ENDS instruction		E								
ENDS technical support			E	E	E	E	E	E		
Structured smoking cessation counselling		x	x	x	x	x	x	x	x	x
OUTCOME MARKERS										
Tobacco use (questionnaires)	x	x	x	x	x	x	x	X*	X*	X*
Estimated ENDS use (ml e-liquids used)			E	E	E	E	E	E*	E*	E*
Exhaled CO		x						x	x	x
Urinary nicotine, cotinine, anabasine		x						x	x	x
Urinary metabolites of nitrosamines (TSNAs)		x						x	x	x
Adverse events, serious adverse events			x	x	x	x	x	X*	X*	X*
VOC and PAH metabolites in urine		x						x	x	x
Oxidative stress markers in urine		x						x	x	x
Oxidative stress in exhaled breath (Lausanne site only)		x						x		
Blood pressure, heart rate, height, weight (BMI), waist circumference		x						x	x	x
Blood lipids, HbA1c (only for participants with diabetes), creatinine		x						x	x	x
Respiratory symptoms		x						X*	X*	X*
Pulmonary function test parameters (FEV1, FVC, FEV1/FVC, PEF, FEF25-75%, TLC, FRC, RV/TLC, DLCO) (Bern site only)		x						x	x	x

Procedure	Screening ①	Baseline visit	Day 0 ①	Week 1 ①	Week 2 ①	Week 4 ①	Week 8 ①	Outcome Visit Month 6	Outcome visit Month 12	Outcome visit Month 24
Multiple breath washout (MBW) parameters (LCI, Scnd, Sacin) (Bern site only)		x						x	x	x
Parameters of ventilation, perfusion and structural changes of the lung (MRI; Bern site only) +								x		
Micronuclei frequency (micronuclei assessment)		x						x	x	x
Olfactory function parameters ((olfactory discrimination score (ODS))		x						x	x	x
“Dry-hit” recognition								E		
Inflammatory biomarkers		x						x		

E: ENDS group only; C: Control group only

* possibility of filling the survey online

+ A aged matched group of healthy never smoking/non-vaping volunteers (N=10) will perform once two consecutive MRI measurements. These volunteers are not participants of the RCT.

